### **6.1.2 *Treatment Period***

- Begins when the subject is assigned to a treatment arm
- Consists of up to 6 eight-week treatment cycles (48 weeks)
  - Nivolumab will be given every 2 weeks
  - Urelumab will be given every 4 weeks
  - On days where both study drugs are given, nivolumab will be given first followed by urelumab within 30 minutes of completing the infusion of nivolumab
  - Subjects may continue additional cycles of study therapy, up to a maximum of 6 cycles, on a case-by-case basis
- This period ends when the subject is discontinued from study therapy

### **6.1.3 *Clinical Follow-up Period***

- Begins from the date the decision was made to discontinue treatment (off treatment date)
- Subjects must be followed for at least 100 days after the last dose
- Follow-up visits should occur at Days 30, 60, and 100 ( $\pm$  7 days) after the last dose or date of discontinuation

### **6.1.4 *Survival/Long-term Period***

- Study subjects will be followed every 3 months to assess survival status
- The duration of survival follow-up will be 3 years following the first dose of study drug
- Subjects who discontinue study drug with ongoing SD, PR, or CR will continue to have tumor assessments every 12 weeks for the first year after discontinuation of study drug, and then continue to receive scans per standard of care guidelines for follow-up or at a minimum of every 6 months up to 3 years following the first dose of study drug, or until disease progression or withdrawal of consent

### **6.1.5 *Re-treatment with Study Therapy***

The consideration to re-initiate study therapy under certain exceptions will be made on a case-by-case basis after considering the overall benefit/risk profile and in consultation between the investigator and the study sponsor. Re-treatment may occur after subjects who complete all 6 cycles of treatment and within 12 months of last treatment. More details are discussed in the Protocol Section 4.5.8.

Subjects entering this phase will receive the study therapy at the same dose levels as assigned at study start and follow the time and events schedule described in the Protocol Tables 5.1-4 to 5.1-6.

All primary efficacy and safety analyses and exposure calculations for the CSR will exclude the re-treatment period, unless otherwise stated. Endpoints which use the date of last study drug as a cut-off refer to the last date of the original treatment period. The SAP and/or DPP may be amended for additional analyses if a substantial number of subjects enter the re-treatment period.

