Subjects who have completed all 6 cycles of treatment and who experience disease progression during the follow-up period after having experienced initial disease control (CR, PR or SD) within 12 months of last treatment with study therapy may be permitted re-initiation of study therapy at their original dose regimen after discussion and agreement with the BMS Medical Monitor. Subjects entering this phase will follow the Time and Events schedule as outlined in [Table 5.1-4](#), [Table 5.1-5](#), and [Table 5.1-6](#). Samples for PK and ADA will be collected as per [Table 5.5.1-3](#), select samples for PD (PBMCs, serum cytokine samples, flow panel samples) will be collected as outlined in [Table 5.7](#).

Subjects undergoing retreatment of study therapy should continue to meet the eligibility criteria with respect to laboratory parameters and organ function at the time study drug resumes and should not have experienced a DLT that would require permanent discontinuation of study therapy.

Screening procedures that need to be repeated are outlined in [Table 5.1-4](#). Subjects will continue to receive study therapy at the same dose levels as assigned at study start. Additional, separate, safety and efficacy listings will be presented for those subjects who reinitiated study therapy.

Subjects who achieve CR during initial therapy and chose to come off therapy for reasons other than toxicity, will be continue to be followed and will be allowed to be re-treated within 12 months of administration of last dose of study drug.

Subjects who experience DLT will not be eligible for retreatment, except as outlined in [Section 4.5.2](#).

4.5.9 *Treatment of Drug Related Infusion Reactions*

Since nivolumab and urelumab contain only human immunoglobulin protein sequences, it is unlikely to be immunogenic and induce infusion or hypersensitivity reactions. However, if such a reaction were to occur, it might manifest with fever, chills, rigors, headache, rash, pruritus, arthralgias, hypo- or hypertension, bronchospasm, or other symptoms. All Grade 3 or 4 infusion reactions should be reported within 24 hours to the BMS Medical Monitor and reported as an SAE if criteria are met. Infusion reactions should be graded according to NCI CTCAE v4.0 guidelines.

Treatment recommendations are provided below and may be modified based on local treatment standards and guidelines as appropriate:

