Physical Examination (PE)	X					A targeted (symptom directed) PE performed by the investigator or designee is required at each subsequent visit.
Performance Status	X	X	X	X		ECOG score prior to dosing (Appendix 4)
Physical Measurements	X	X	X	X		Weight only prior to dosing
Vital Signs	X	X	X	X		
Vital signs (body temperature, seated blood pressure, heart rate and respiratory rate) will be obtained before the BMS-936558 infusion, after the BMS-936558 infusion, before the BMS-663513, and after the BMS-663513 infusion.
 
Subjects must be observed for 30 minutes after the BMS-663513 infusion before discharge. If any vital sign is abnormal at the final check, the subject must be observed further for a period of time, as clinically indicated.
 
The start and stop time of the study drug infusion should be documented. If there are any new or worsening clinically significant changes since the last examination, report changes on the appropriate non-serious or serious adverse event page.
 
See Section 4.5.9 for treatment of infusion reaction.

Non-Serious Adverse Events	X	X	X	X		Non-serious AEs will be collected starting with the first dose of study medication and through 100 days after discontinuation of dosing.
Serious Adverse Events	X	X	X	X		All SAEs must be collected starting at the time a subject signs informed consent and through 100 days after discontinuation of dosing. SAEs should be approved in TAO within 5 business days of entry
	■	■	■	■		■■■■■

Table 5.1-5: Retreatment Procedural Outline (CA186107)

Procedure	Cycles 1-6					Notes
	D 1a (-2 days)	D 15 (± 2 days)	D 29 (± 2 days)	D 43 (± 2 days)	D 49-56	
Chest Radiograph						As clinically indicated.
Oxygen Saturation Levels	X	X	X	X		Collected pulse oximetry at rest prior to dosing.
Laboratory Tests	X	X	X	X		On study labs (including pregnancy testing) to be done on site/local. Within 72 hrs prior to dosing
Chemistry (excluding LFTs)	X	X	X	X		For all visits includes assessments for sodium, potassium, chloride, total serum calcium, magnesium, carbon dioxide, phosphorus, BUN, creatinine, glucose, total protein, albumin, amylase, lipase, CRP, ferritin, and LDH.
CBC with differential & platelets	X	X	X	X		Should also be collected at each timepoint where samples for immunophenotyping are collected as listed in Table 5.7-1

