8.3.1 Primary Endpoint(s)

The primary objective (to assess the safety and tolerability of urelumab given in combination with nivolumab and to identify dose limiting toxicities (DLTs) and the maximally tolerated dose (MTD) of the combination) will be measured by the following primary endpoints.

- a) Incidence of adverse events: all non-serious adverse events will be collected from Day 1 until 100 days after the subject's last dose of study drug or until they discontinue the study as per [Section 3.5](#). All serious adverse events must be collected from the date of the subject's written consent until 100 days after discontinuation of dosing or until they discontinue the study as per [Section 3.5](#).
- b) Incidence of clinical laboratory test abnormalities including hematology and serum chemistry, and thyroid panel abnormalities, assessed at specified time points as designated in the Time and Events [Section \(5.1\)](#).

Assessments will be based on adverse event reports and the results of vital sign measurements, electrocardiograms (ECGs), physical examinations, imaging studies, and clinical laboratory tests. Adverse events will be categorized using the most current version of the Medical Dictionary for Regulatory Activities (MedDRA); both AEs and laboratory tests will be graded using NCI CTCAE v4.0. All subjects who receive study drug therapy will be evaluated for safety as measured by the rate of adverse events (AEs), and serious adverse events (SAEs), and will be assessed during treatment and for 100 days in follow-up.

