## 4 ENDPOINTS

### 4.1 Primary Endpoint

All subjects who receive at least one (full or partial) dose of urelumab or nivolumab will be evaluated for safety as measured by the occurrence of adverse events (AEs), serious adverse events (SAEs), deaths, and laboratory abnormalities. All non-serious AEs will be assessed from the start of dosing. All SAEs and deaths will be assessed from the date of the subject's written informed consent. All AEs (serious and non-serious), and deaths will be assessed up to 100 days after the subject's last dose of study drug or until they discontinue the study as per Protocol Section 3.5. Incidence of clinical laboratory abnormalities will be assessed at specified timepoints described in Protocol Section 5.1.

In addition, the occurrence of abnormalities in vital signs, electrocardiograms (ECGs), physical examinations, and clinical laboratory tests will be examined.

Adverse events will be categorized using the most current version of the Medical Dictionary for Regulatory Activities (MedDRA) at the time of each database lock; both AEs and laboratory values will be graded according to the National Cancer Institute (NCI) Common Terminology Criteria for Adverse Events (CTCAE) version 4.0.

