### **7.6.1 Deaths**

#### **Summary:**

- All deaths during the study within 100 days after the last dose of either study drug will be summarized for cause of deaths by treatment group.

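### The SAP excludes re-treatment from every adverse event and laboratory summary, so a death or Hy's Law-type case in a second course can be missing from the primary safety tables

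*SAP*

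**What the plan says.** Safety is the primary endpoint. Protocol 8.3.1 states that "all non-serious adverse events will be collected from Day 1 until 100 days after the subject's last dose of study drug". SAP 4.1 uses the same window: "All AEs (serious and non-serious), and deaths will be assessed up to 100 days after the subject's last dose of study drug". Neither limits the last dose to the first course. Protocol Table 5.1-5, the re-treatment schedule, keeps collection going: "Non-serious AEs will be collected starting with the first dose of study medication and through 100 days after discontinuation of dosing". Protocol 8.4.3 puts every recorded adverse event into tables as well as listings and mentions no exception.

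SAP 6.1.5 then narrows the analysis: "All primary efficacy and safety analyses and exposure calculations for the CSR will exclude the re-treatment period, unless otherwise stated". Its next sentence ties last-dose cut-offs to the original course: "Endpoints which use the date of last study drug as a cut-off refer to the last date of the original treatment period". SAP 7.6 repeats the exclusion for adverse event and laboratory summaries, and SAP 7.4 for exposure. No safety summary in the SAP makes an exception. SAP 7.6.1 says: "All deaths during the study within 100 days after the last dose of either study drug will be summarized".

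On reporting the second course, Protocol 4.5.8 says: "Additional, separate, safety and efficacy listings will be presented for those subjects who reinitiated study therapy". The SAP names only subject-status listings for it (7.3.1). Under 6.1.5, anything further is optional and depends on enough subjects being re-treated, with no figure for how many.

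**The concern.** Re-treatment is a second exposure to the same combination at the original dose, for up to six more cycles. The main known risk of urelumab is hepatotoxicity. A reader of the clinical study report will take the adverse event, death and hepatic tables as the answer to the primary objective, but under the SAP they answer it for the first course only.

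The Hy's Law count is where this matters most. Protocol 1.5 makes two such events, occurring at any time in the study, decisive for whether a cohort and those above it exceed the MTD, and identifying the MTD is part of the primary objective. SAP 7.6.7.1 tabulates concurrent ALT or AST above 3 x ULN with bilirubin above 2 x ULN, but SAP 7.6 keeps re-treatment results out of laboratory summaries. A case could count toward the protocol's rule and be missing from the table meant to show such cases. A trigger based on how many subjects are re-treated does not protect against this, because one or two events are enough.

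**Working it through.** The plan states no figure for this point, so there is none to reproduce. The check is a comparison of rules plus day counts.

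**1. What each SAP output does with re-treatment**

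| SAP output | Rule | Re-treatment events |
|---|---|---|
| AE summaries, 7.6 | excluded in 6.1.5 and again in 7.6 | out |
| Laboratory summaries, including hepatic, 7.6 and 7.6.7 | same | out |
| Exposure, 7.4 | excluded | out |
| Death summary, 7.6.1 | 100-day cut-off, read with 6.1.5; exclusion not repeated | out if later than 100 days after the original last dose; unclear if earlier |
| Death listing, 7.6.1 | all recorded deaths, no time limit | in |
| SAE listing, 7.6.2 | all enrolled subjects, no period limit stated | in |
| AE listing, 7.6.4 | pretreatment, on-treatment and post-treatment periods | not named |
| Hepatic listing, 7.6.7.1 | the abnormalities in the hepatic table | not named |
| Re-treatment listings, 7.3.1 | subject status | status only |

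The express exclusion does most of the work. The reset of the last dose mainly affects the death table.

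**2. How much observation is involved**

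Inputs: six 8-week cycles with nivolumab last given on Day 43 of a cycle (Protocol 3.1.2), and the follow-up formula in SAP 7.6.6, last dose minus first dose + 100 + 1 days.

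- Last planned dose: 5 x 56 + 43 = day 323.
- Original window: 323 - 1 + 100 + 1 = 423 days (423 / 365.25 = 1.16 years), ending on day 423.
- A full second course has its own 423-day window.
- Second course starting 30 days after the last dose (day 353): 423 - 353 + 1 = 71 days lie inside the original cut-off by date.
- Starting 60 days after (day 383): 423 - 383 + 1 = 41 days inside.
- Starting 101 days after or later (day 424 onward): none inside; all 423 days fall outside.

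So the cut-off alone would keep some early re-treatment events. For AEs and laboratory values the express exclusion removes those too. For deaths in that overlap, SAP 7.6.1 does not say.

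**3. Effect on subject-level incidence (illustration only)**

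The number re-treated is not given. Let r be the share re-treated and p the chance of a given event per course. With independent courses, the omitted incidence is r x p x (1 - p). Take r from 2% to 10% (assumed) and p from 2% to 6%. The p range uses this combination's own data in Protocol 1.5: Grade 3/4 ALT and AST elevations 2% each, related events leading to discontinuation 6%.

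- Low: 0.02 x 0.02 x 0.98 = 0.0004, or 0.04 percentage points.
- High: 0.10 x 0.06 x 0.94 = 0.0056, or 0.56 percentage points.

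Independence is doubtful, since subjects with a DLT are generally ineligible for re-treatment (Protocol 4.5.8). These figures show only that the average shift is not the argument.

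**4. Why the two courses should not be pooled into one window**

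Re-treatment may start up to 12 months after the last treatment, while routine non-serious AE collection stops 100 days after dosing. For a start 365 days after the last dose (day 688), collection lapses from day 424 to day 687, which is 264 days. The last re-treatment dose falls on day 688 + 322 = 1010. The SAP 7.6.6 formula over both courses gives 1010 - 1 + 100 + 1 = 1110 days, against 423 + 423 = 846 days of routine collection. The difference is the same 264 days, which would count as exposure and bias rates downward.

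**The case against.** The strongest reply is that this is a disclosed analysis choice. Protocol 8.3.1 governs collection, the protocol itself sets re-treated subjects apart for reporting, and the SAP states its restriction openly and removes exposure along with events. The study is descriptive, with no formal hypothesis, and a first-course analysis is legitimate. SAP 9 leaves the complete list of analyses to a Data Presentation Plan that is not among the documents, so re-treatment outputs may be specified there.

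Much of this stands. The original-course tables should stay, and the collection wording in 8.3.1 does not by itself contradict the SAP. The reply does not remove the tension with Protocol 8.4.3, which tabulates all recorded events, or the mismatch between the SAP's own endpoint window in 4.1 and its tables. The protocol calls the re-treatment listings additional, which does not mean a replacement for tabulation, and the SAP does not name them.

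A reader might infer three stronger things that the documents do not support:

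- **That events are lost or hidden.** Collection continues through re-treatment, and all recorded deaths and SAEs are listed.
- **That the tables can only understate risk.** This holds for the share of subjects with an event. It fails for the rates per 100 person-years in SAP 7.6.6, where re-treatment leaves both numerator and denominator. Re-treated subjects are also selected for disease control and tolerance, so the direction is not fixed.
- **That the shift is large, using the 27.5% rate of related Grade 3 or higher events in Protocol 1.4.3.** That rate comes from urelumab monotherapy studies in which doses reached 15 mg/kg (Protocol 1.4.3.1). Protocol 1.5 equates this trial's 8 mg with about 0.1 mg/kg.

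**Conclusion.** The concern holds as a reporting gap in the primary safety analysis. Under stated SAP rules, AEs and laboratory abnormalities on re-treatment are in no summary. A death more than 100 days after the original last dose is outside the death table even if it occurs on study drug. An earlier death on re-treatment is handled ambiguously. The separate safety listings promised by the protocol are not named in the SAP.

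The effect on incidence cannot be stated without the number re-treated. For a subject who receives a full second course, up to 423 days of AE observation are unsummarised, assuming six complete cycles dosed on schedule. The importance lies in single serious events, above all deaths and Hy's Law-type cases. The conclusion rests on the SAP as written; a Data Presentation Plan that already specifies these outputs would narrow it.

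**What to change.** Keep the original-course tables and amend SAP 6.1.5 and 7.6 as follows:

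- Add a separate re-treatment summary of AEs, SAEs, deaths and hepatic laboratory abnormalities, from the first re-treatment dose to 100 days after the last re-treatment dose. Use re-treated subjects and re-treatment exposure as denominators.
- Report one study-wide count of deaths and Hy's Law-type cases across both periods, so that it can be set against Protocol 1.5.
- Name the safety and efficacy listings promised in Protocol 4.5.8.
- State in SAP 7.6.1 which last dose applies, and how a death on re-treatment within 100 days of the original last dose is counted.
- Drop the condition on the number re-treated for these outputs.
- Do not merge both courses into one continuous exposure window.

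The cost is a few extra tables from data already collected. Their denominators will be small, so they should be read as counts rather than as stable rates.

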## **6.2 Treatment Regimens**

Refer to [Table 2](#) and [Table 4](#) for treatment arms explored in this trial. Some of these arms might not have any subjects.

Certain analyses (eg, PFS and DOR) may include subjects in the dose escalation phase and subjects in the cohort expansion phase matched by disease type and regimen.

The treatment group “as assigned” will be retrieved from the IVRS system, if applicable. The treatment group “as treated” will be the drug combination that the subject actually received during the study, even if it is not the same as the arm that was assigned by IVRS. Unless otherwise specified, the safety analysis will be based on “as treated”.

## **6.3 Populations for Analyses**

- All Enrolled Subjects: All subjects who sign an ICF and are registered into IVRS will be included. Subject disposition will be tabulated using this dataset.
- All Treated Subjects: All subjects who receive at least one dose of either study drug. This population will be used for safety and efficacy analyses unless otherwise specified.
- Response Evaluable Subjects: All treated subjects who receive either study drug, have a baseline tumor assessment with measurable disease, and one of the following:
  - At least one evaluable on-treatment tumor assessment prior to subsequent therapy
  - Clinical progression prior to subsequent therapy
  - Death, if death occurred within 100 days after last dose
- Urelumab PK Subjects: All subjects who receive at least one dose of urelumab and have adequate serum concentration data for urelumab PK.
- Nivolumab PK Subjects: All subjects who receive at least one dose of nivolumab and have adequate serum concentration data for nivolumab PK.
- Urelumab ADA Evaluable Subjects: All subjects who receive at least one dose of urelumab with baseline and at least 1 post-baseline urelumab immunogenicity assessment.
- Nivolumab ADA Evaluable Subjects: All subjects who receive at least one dose of nivolumab with baseline and at least 1 post-baseline nivolumab immunogenicity assessment.
- Biomarker Evaluable Subjects: All Treated Subjects with at least one evaluable measurement for a specific marker will be included in the dataset for that marker. Evaluable may differ depending on the analysis. All subjects in the biomarker dataset with baseline measurement and at least one on-treatment measurement will be included in PD analyses. Predictive biomarker analyses will be performed on all subjects in the biomarker dataset with corresponding efficacy measurement.

## **7 STATISTICAL ANALYSES**

### **7.1 General Methods**

All analyses will be performed in SAS using version 9.2 or higher. Some figures may be generated using S-Plus.

Continuous variables will be summarized by treatment group using the mean, standard deviation, median, minimum, and maximum values. Some continuous variables may also be summarized

using the geometric mean and coefficient of variation. Categorical variables will be summarized by frequencies and percentages. Percentages will be rounded and may not always add up to 100. Percentages less than 0.1 will be indicated as “< 0.1”.

In general, all analyses will be presented by tumor type and treatment group, unless otherwise specified. There will be 9 categories: NSCLC-NAIVE, MEL, SCCHN, DLBCL, NSCLC-PROG, FL, Other Solid, Other Blood, and All Comers, where sufficient data is available, unless otherwise specified.

